## 4 STUDY POPULATION

### 4.1 Inclusion Criteria

Each subject must:

1. Be male or female  $\geq 18$  years of age.
2. Provide written informed consent and be willing and able to adhere to the study-specified procedures and restrictions. NOTE: Consent may be provided by the subject's legally authorized representative in accordance with local regulations.
3. Have an acute illness ( $\leq 7$  days duration) with at least 3 of the following symptoms consistent with a lower respiratory tract infection (new or worsening):
  - Dyspnea.
  - New or increased cough.
  - Purulent sputum production.
  - Chest pain due to pneumonia.
4. Have at least 2 of the following vital sign abnormalities:
  - Fever (body temperature  $>38.0^{\circ}\text{C}$  ( $100.4^{\circ}\text{F}$ ) measured orally or equivalent temperature from an alternate body site) or hypothermia (body temperature  $<35.0^{\circ}\text{C}$  ( $95.0^{\circ}\text{F}$ ) measured orally or equivalent temperature from an alternate body site).
  - Hypotension (systolic blood pressure  $<90$  mmHg).
  - Tachycardia (heart rate  $>100$  beats/min).
  - Tachypnea (respiratory rate  $>20$  breaths/min).
5. Have at least 1 other clinical sign or laboratory finding of CABP:
  - Hypoxemia (i.e.,  $\text{O}_2$  saturation  $<90\%$  on room air or while receiving supplemental oxygen at subject's baseline requirement or  $\text{PaO}_2 <60$  mmHg).

- Auscultatory and/or percussion findings consistent with pneumonia (e.g., crackles, egophony, dullness).
  - White blood cell (WBC) count  $>10,000$  cells/mm^3 or  $<4500$  cells/mm^3 or  $>15\%$  immature neutrophils (bands) regardless of total WBC count.
6. Have radiographically-documented pneumonia within 48 hours before enrollment (i.e., infiltrates in a lobar or multilobar distribution or diffuse opacities on chest x-ray or chest computed tomography scan consistent with acute bacterial pneumonia).
  7. Have a Pneumonia Outcomes Research Team (PORT) Risk Class  $\geq$ III and require IV antibiotic therapy as initial treatment for the current episode of CABP.
  8. If female, meets the following criteria:

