  - Receipt within 7 days before enrollment of Class IA or Class III anti-arrhythmic medication or, in the opinion of the Investigator, subject may require such medication during the study. (Class 1A: Quinidine, Procainamide, Disopyramide; Class III: Amiodarone, Dofetilide, Ibutilide, Sotalol)
  - Receipt within 7 days before enrollment of medication that has the potential of prolonging the QT interval or, in the opinion of the Investigator, subject may require such medication during the study (see Appendix 5).
9. Be receiving a strong p-glycoprotein inhibitor or a strong CYP3A inducer or inhibitor (see Appendix 4)
10. Have a history of tendon disease/disorder, myasthenia gravis, or known or suspected central nervous system (CNS) disorders (severe cerebrovascular arteriosclerosis, epilepsy, or other risk factors that may predispose to seizures).
11. Have a history of any hypersensitivity or allergic reaction to any fluoroquinolone or any drug in the pleuromutilin class (i.e., retapamulin).
12. Have severely impaired renal function, defined as creatinine clearance (CrCl)  $\leq 30$  mL/min as calculated by the Cockcroft-Gault formula.

13. Have evidence of significant hepatic, hematologic, or immunologic disease including any of the following:
  - Known acute hepatitis, including active viral hepatitis.
  - Aspartate aminotransferase (AST) or alanine aminotransferase (ALT) level >5 times the upper limit of normal (ULN) or total bilirubin >3 times the ULN.
  - Aspartate aminotransferase (AST) or alanine aminotransferase (ALT) level >3 times the upper limit of normal (ULN) and total bilirubin >2 times the ULN.
  - History of cirrhosis of the liver.
  - Manifestation of end-stage liver disease, such as ascites or hepatic encephalopathy.
  - Current or anticipated neutropenia (<500 neutrophils/mm^3).
  - Thrombocytopenia (<50,000 platelets/mm^3).
  - Known infection with human immunodeficiency virus and a CD4 count <200/mm^3.
14. Have known or suspected severe immunosuppression, defined as receipt of corticosteroid therapy ( $\geq 20$  mg prednisone/day or equivalent for more than 4 weeks) within the previous 8 weeks; solid organ or bone marrow transplantation within the previous 12 months; or currently receiving cytotoxic chemotherapy.

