## 9.7 Safety Analysis

Safety will be evaluated in the Safety Analysis Set by presenting summaries of AEs, routine clinical laboratory evaluations, ECGs, and vital signs in the 2 treatment groups. Subjects who receive the wrong study drug for their entire course of treatment will be analyzed in the group based on the drug received.

Summary tables will be provided for all TEAEs. A TEAE is defined as an AE with a start date and time on or after the first dose of study drug. Adverse events will be coded using the Medical Dictionary for Regulatory Activities (MedDRA®). The number and percentage of subjects with TEAEs will be tabulated by system organ class (SOC) and MedDRA Preferred Term for each treatment group and by severity and relationship to treatment.

Adverse events leading to premature discontinuation from the study drug and serious TEAEs will be presented either in a table or a listing.

Change from baseline to each scheduled evaluation and the overall worst post-baseline in clinical laboratory variables will be summarized by treatment group. The number and percent of subjects with treatment-emergent potentially clinically significant (PCS) laboratory values will be tabulated for each treatment group. Treatment-emergent PCS laboratory tests are those in which the Baseline value is not PCS and the post-baseline value is PCS. PCS will be defined based on the pre-specified criteria outlined in the statistical analysis plan.

Change from baseline to each scheduled evaluation and the overall worst post-baseline for RR interval, PR interval, QRS interval, QT interval, and QT interval corrected with Fridericia from the ECG will be summarized for each treatment group with the mean, standard deviation, minimum value, and maximum value. The triplicate values will be averaged for each subject before analysis. An outlier analysis will also be provided based on the worst post-baseline value.

Descriptive statistics of vital signs and the change from baseline to each scheduled evaluation will be summarized by treatment group at each study visit and the worst overall post-baseline. The number and percent of subjects with treatment-emergent PCS values will be tabulated for each treatment group.

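### The treatment-emergent PCS laboratory count omits subjects already PCS at baseline who worsen further on study drug

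*Protocol*

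**What the plan says.** Protocol Section 9.7 defines the laboratory count: "Treatment-emergent PCS laboratory tests are those in which the Baseline value is not PCS and the post-baseline value is PCS". The cut-offs are deferred: "PCS will be defined based on the pre-specified criteria outlined in the statistical analysis plan". The definition has no category for a value that is PCS at baseline and then gets worse.

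For vital signs, the same section says "The number and percent of subjects with treatment-emergent PCS values will be tabulated for each treatment group", but does not define treatment-emergent separately for them.

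Section 9.7 also plans a summary without any baseline condition: "Change from baseline to each scheduled evaluation and the overall worst post-baseline in clinical laboratory variables will be summarized by treatment group".

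On entry, Section 4.2 (Exclusion 13) removes subjects with "Aspartate aminotransferase (AST) or alanine aminotransferase (ALT) level >5 times the upper limit of normal (ULN) or total bilirubin >3 times the ULN", those with AST/ALT above 3 x ULN together with bilirubin above 2 x ULN, and those with platelets below 50,000/mm³. Values short of these limits are admissible. Section 4.1 (Inclusion 5) asks for at least one further sign or laboratory finding, and an abnormal WBC or band count is one of three ways to satisfy it. Inclusion 4 reads "Have at least 2 of the following vital sign abnormalities".

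**The concern.** The counting rule looks only for a crossing from not PCS to PCS. It suits subjects who start within limits. In this trial some subjects may start beyond them, because acute pneumonia disturbs laboratory values and the entry criteria leave room for that. A subject who is PCS at baseline and deteriorates sharply is treated, for that test, in the same way as one who stays stable or recovers: none of them is counted.

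At stake is the completeness of the by-arm laboratory comparison. Section 9.7 describes no other laboratory output that counts subjects by arm. Section 1.5.3 calls this the first Phase 3 study of a systemically administered pleuromutilin, and Section 7.5 singles out liver tests for special reporting. A count of individual worsening that includes subjects with impaired baseline values is therefore worth having.

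**Working it through.** The protocol states no PCS cut-off and no share of subjects who are PCS at baseline, so there is no figure to reproduce. The check applies the written rule to example subjects over a range of assumed cut-offs.

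**Rule as written.** For baseline value b, worst post-baseline value w and upper cut-off t: counted if b ≤ t and w > t.

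**ALT, in multiples of ULN** (Exclusion 13 removes values above 5; cut-offs are assumptions):

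| Assumed PCS cut-off | 2.5 to 12 | 4 to 12 | 5 to 12 |
|---|---|---|---|
| >2 | not counted | not counted | not counted |
| >3 | counted | not counted | not counted |
| >5 | counted | counted | counted |
| >8 | counted | counted | counted |
| >10 | counted | counted | counted |

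With a cut-off of >3 x ULN, a rise from 4 to 12 x ULN (a tripling) is missed. With >5 x ULN or higher, no eligible subject is PCS at the value used for eligibility, so the gap nearly closes. It may not close entirely: Section 6.12 has local eligibility bloods repeated centrally after enrollment, and the central value may differ.

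**Other tests, by the same logic:**
- Bilirubin: the gap is open for any cut-off below 3 x ULN.
- Platelets: it is open for any low cut-off above 50,000/mm³.
- WBC: Exclusion 13 sets no numerical upper limit, so no high cut-off rules out a PCS baseline.

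**Vital signs.** Section 9.7 states the definition for laboratory tests only. If it were carried over to heart rate, where Inclusion 4 uses >100 beats/min:

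| Assumed PCS cut-off | 105 to 135 | 118 to 140 | 125 to 140 |
|---|---|---|---|
| >100 | not counted | not counted | not counted |
| >110 | counted | not counted | not counted |
| >120 | counted | counted | not counted |
| >130 | counted | counted | counted |

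The result again depends on the cut-off. An entry-level abnormality is not in itself a PCS baseline.

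**What the other safety outputs supply:**
- Change-from-baseline and worst-value summaries (Section 9.7) include every subject. They are group-level and do not say how many worsened.
- Potential Hy's Law reporting (Section 7.5) has no baseline condition, but needs AST/ALT above 3 x ULN and bilirubin above 2 x ULN. An isolated rise in ALT or fall in platelets does not qualify.
- Adverse event reporting (Section 7) covers worsened conditions, but a laboratory abnormality qualifies only if it has clinical signs or symptoms or needs medical intervention.
- The ECG outlier analysis (Section 9.7) uses the worst post-baseline value and states no baseline condition.

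None of these gives the number of subjects per arm whose laboratory value worsened from a PCS baseline.

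**The case against.** The strongest reply is that everything turns on the SAP's cut-offs. If they lie beyond the entry limits, or include a change-from-baseline component, few or no subjects are PCS at baseline and the rule loses little. This stands, and it is why no size can be given. It does not remove the point: the protocol fixes the crossing rule, and an SAP that follows that definition as written cannot count worsening from a PCS baseline.

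Second, crossing from not PCS to PCS is a plain reading of treatment-emergent, and shift tables are display detail usually left to an SAP. This also stands: the lack of a shift table in the protocol is no fault. The point concerns the rule that is stated.

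Third, other outputs would show a severe case. Section 9 plans minimums and maximums, so the most extreme value would appear in the worst-value summary, and the DMC reviews safety by masked arm. This is correct, and it limits the gap to one table. Detection of serious harm does not depend on that table.

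Three stronger readings are tempting but unsupported:
- A reader might infer that any subject who enters abnormal and worsens is never counted. The rule turns on a PCS baseline, and the omission applies to this table only.
- A reader might infer that, because Inclusion 4 requires 2 of 4 signs abnormal, at least 2/4 = 50% of subject-by-sign records can never become treatment-emergent. That assumes PCS limits equal to the entry limits and a definition that the protocol does not state for vital signs. It also overlooks that a sign abnormal in one direction may become PCS in the other.
- A reader might infer that the treatment comparison is biased. The same rule applies to both randomized, blinded arms, and nothing in the protocol shows a differential effect.

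**Conclusion.** The point holds in a narrow form. By the definition in Section 9.7, the by-arm treatment-emergent PCS laboratory count leaves out subjects who are PCS at baseline and worsen further. The entry criteria allow such subjects, but how many there will be cannot be computed from the protocol. For ALT the loss is largely absent with a cut-off above 5 x ULN and real with one at 2 or 3 x ULN. For vital signs the protocol leaves the definition open, so there the matter is an ambiguity to resolve. The consequence is an incomplete descriptive safety table. It is an inexpensive improvement, and the primary efficacy conclusions are untouched.

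**What to change.** Revise the definition in Section 9.7 and carry it into the SAPs, which Section 9 says are to be finalized before database lock:

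1. Count a post-baseline PCS value as treatment-emergent if the baseline value was not PCS, or if the value has worsened from a PCS baseline by an amount pre-specified in the SAP (for example one severity category, or a doubling for AST/ALT).
2. State whether the same definition applies to the vital-sign PCS table, given that Inclusion 4 requires at least 2 abnormal signs at entry.
3. Show worsening from a PCS baseline by arm, for example in a baseline-to-worst shift table, so that it can be told apart from new PCS values.

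No new data are needed. The cost is a change of wording and minor programming. PCS counts will rise somewhat in both arms, and the separate display in item 3 lets a reader see why.

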## 9.8 Handling of Missing Data

For the primary outcome measure (FDA), if any data field needed to determine ECR is missing, the subject will be assigned a response of Indeterminate. For analyses of the primary outcome, subjects with an indeterminate response are included in the denominator, and thus are considered Non-responders. A sensitivity analysis of the primary outcome will be conducted in which subjects with an indeterminate response are considered Responders.

For the outcome measure of IACR at EOT, TOC, and LFU, missing data are considered as a response of Indeterminate. For analysis in the ITT, mITT and microITT Analysis Sets, indeterminate outcomes are included in the denominator and are thus, considered clinical Failures. By definition, subjects with an IACR of Indeterminate are excluded from the CE-EOT, CE-TOC, CE-LFU, ME-EOT, ME-TOC, and ME-LFU Analysis Sets.

A missing microbiological response is considered a presumed response based on the IACR. For analysis in the microITT Analysis Set, indeterminate outcomes are included in the denominator and are thus, considered microbiological failures. By definition, subjects with an IACR of Indeterminate are excluded from the ME Analysis Sets.

Handling of missing data for other efficacy and safety outcomes will be presented in the SAP.

## **9.9 Interim Analysis and Independent Interim Analysis Committee (IAC)**

In order to ensure that the point estimate of the ECR responder and IACR success rates used in the estimation of the sample size is valid for this study, an interim analysis for sample size re-estimation will be performed when ECR data at  $96 \pm 24$  h post first dose are available for approximately 60% of randomized subjects (330 subjects) (see Section 9.4.1). The draft FDA Guidance “Non-inferiority Clinical Trials” notes that such a sample size re-estimation if based on the blinded overall response rates is not only acceptable but is advisable. The interim analysis will involve a sample size re-estimation to either confirm the initial sample size estimate is adequate or increase the sample size (number of randomized subjects) to ensure the study has adequate power for determining whether lefamulin is non-inferior to moxifloxacin for the primary outcome measures for the FDA and EMA. The sample size re-estimation will be based on the blinded overall (not by treatment group) ECR responder rate and will be conducted by an independent, blinded statistician.

An Independent Interim Analysis Committee (IAC) will be provided the results of the interim analysis by the independent, blinded statistician and make a recommendation regarding any increase to the sample size. The IAC will consist of 3 members who will be selected by the Sponsor but will be independent from the Sponsor, will not participate in the study as Principal or Co-investigators, and should be isolated from the study if their institution is a study site. The IAC members receive no financial incentives for their participation, but are reimbursed only for customary consultative and administrative support fees. A detailed IAC charter outlines the analyses to be completed, statistical rules, the potential increase to the sample size and the recommendations that can be made to the Sponsor.

The members of the IAC will not participate in the ongoing assessment of the important aspects of study conduct, including the assessment of safety data. This will be conducted by a separate Data Monitoring Committee (DMC) as outlined in Section 10.2.

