### **Statistical Considerations:**

Sample Size: Utilizing an anticipated ECR responder rate of 79% in the ITT Analysis Set, and a one-sided alpha of 0.025, a sample size of 550 subjects (275 in each treatment group) provides >90% power to establish the non-inferiority (NI) of lefamulin to moxifloxacin for ECR using a NI margin of 12.5% at the ECA. Assuming an IACR success rate of 80% and 85% in the mITT and CE-TOC Analysis Sets, respectively, and a clinical evaluability rate of 80%, there is 80% power for demonstration of NI for IACR at the TOC Visit using a 10% NI

margin. However, if based upon regulatory requirements additional subjects exposed to lefamulin are needed, up to 626 subjects may be enrolled. This sample size provides >95% power for demonstration of NI for ECR and 85% power for demonstration of NI for IACR at the TOC Visit.

Treatment Comparison of Interest: All comparisons will be for lefamulin vs. comparator therapy (moxifloxacin ± linezolid).

Interim Analysis: In order to ensure that the point estimate of the ECR responder and IACR success rates used in the estimation of the sample size are valid for this study, an interim analysis for sample size re-estimation will be performed when ECR data at  $96 \pm 24$  hours post first dose are available for approximately 60% of randomized subjects (330 subjects). An independent statistician will provide the Independent Interim Analysis Committee (IAC) with the results of the interim analysis; the IAC will make a recommendation regarding any potential increase to the planned sample size.

Analysis Populations:

- *Intent-to-treat (ITT) Analysis Set:* All randomized subjects regardless of whether or not the subject received study drug. A subject is considered randomized when an IRT-generated randomization number has been assigned.
- *Modified ITT (mITT) Analysis Set:* All randomized subjects who receive any amount of study drug. Subjects are analyzed based on the randomized (i.e., assigned) treatment group.
- *Microbiological ITT (microITT) Analysis Set:* All subjects in the ITT Analysis Set who have at least one baseline “typical” bacterial pathogen known to cause CABP, *Legionella pneumophila* from an appropriate microbiological specimen, or who have CABP caused by *Mycoplasma pneumoniae* or *Chlamydomphila pneumoniae*.

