## 9.2 Sample Size Determination

A total of 550 subjects will be randomized in this study (275 subjects in each treatment group). However, if based upon regulatory requirements additional subjects exposed to lefamulin are needed, up to 626 subjects may be enrolled. The total number of subjects included in this study is sufficient to achieve the primary and secondary study objectives based on statistical considerations.

Retrospective analyses of clinical study data for patients with CABP of varying severity indicate the point estimates for an ECR responder at Days 3-5 range from 72%-81% (FDA, 2011). Thus, it is reasonable to assume that in a prospective study of subjects with CABP, the proportion of subjects who are responders for ECR at  $96 \pm 24$  hours post first dose of study drug will be approximately 79%.

The primary efficacy analysis variables used for NI analyses for the Marketing Authorization Application (MAA) to the EMA will be the proportion of subjects with an IACR of Success at TOC in the mITT and CE-TOC Analysis Sets. In recent clinical studies, IACR success rates at the TOC Visit in the CE Analysis Set ranged from 77%-87% depending on the antibiotics under study and the severity of the CABP. The IACR success rate for subjects receiving moxifloxacin is 86% as reported in the prescribing information (AVELOX® [moxifloxacin] PI, 2013). Based on these data, an 85% IACR success rate in the CE-TOC Analysis Set was chosen for determination of the sample size. The success rate is expected to be about 5% lower in the mITT Analysis set. It is expected that <1% of subjects will be excluded from the mITT Analysis Set and thus, the sample size determination assumes the same number of subjects in the ITT and mITT Analysis Sets.

Utilizing an anticipated ECR responder rate of 79% in the ITT Analysis Set, and a one-sided alpha of 0.025, a sample size of 550 subjects (275 in each treatment group) provides >90% power to establish the NI of lefamulin to moxifloxacin for ECR using a NI margin of 12.5% at the ECA. Assuming an IACR success of 80% and 85% in the mITT and CE-TOC Analysis Sets, respectively, and a clinical evaluability rate of 80%, there is 80% power for demonstration of NI for IACR at the TOC Visit using a 10% NI margin. If the sample size is

increased to 626 subjects, it will provide >95% power for demonstration of NI for ECR and 85% power for demonstration of NI for IACR at the TOC Visit.

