Additional analyses of the primary efficacy analysis will be conducted. ECR will be assessed separately across the geographic regions, prior antibiotic use, and PORT risk class strata. For each geographic region, prior antibiotic use, and PORT risk class stratum, a 2-sided 95% CI for the observed difference in ECR responder rates will be calculated for the ITT Analysis Set. Sensitivity analyses of ECR include determination of an adjusted 95% CI (adjusted for the randomization stratification factors) and considering all subjects with missing data (i.e., Indeterminates) at  $96 \pm 24$  hours after the first dose of study drug as responders for ECR (these subjects are considered non-responders in the primary analysis). For the second sensitivity analysis, an unstratified 95% CI will be computed for the difference in the responder rates between lefamulin and moxifloxacin. Subgroup analyses of the primary efficacy outcome will also be conducted for descriptive purposes and will be detailed in the SAP.

For the EMA primary analysis (secondary analysis for the FDA), the number and percentage of subjects in each treatment group with an IACR of Success, Failure and Indeterminate (by definition Indeterminates are not included in the CE-TOC Analysis Set) at TOC will be reported in the mITT and CE-TOC Analysis Sets. Subjects who have an IACR of Failure at EOT will be considered to have an IACR of Failure at TOC. The primary analysis for the EMA will utilize 2-sided adjusted (for the randomization stratification factors) 95% CIs calculated using the method of Miettinen-Nurminen. If the lower limit of the 95% CI for the difference in success rates in both the mITT and CE-TOC Analysis Sets is greater than -10%, the NI of lefamulin to moxifloxacin will be concluded. Two-sided unstratified 95% CIs will be calculated for the difference in success rates at TOC in the mITT and CE-TOC Analysis Sets (FDA secondary outcome).

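### Section 9.9 says the interim secures power for both the FDA and EMA primary outcomes, but its only stated input is the pooled ECR rate

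*Protocol*

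**What the plan says.** Section 9.9 gives the interim two purposes. The first is to confirm that "the point estimate of the ECR responder and IACR success rates used in the estimation of the sample size" is valid. The second is to confirm or raise the sample size so that there is adequate power to show that lefamulin is "non-inferior to moxifloxacin for the primary outcome measures for the FDA and EMA". The Synopsis (Statistical Considerations, Interim Analysis) repeats the first purpose: the look is there to ensure that "the ECR responder and IACR success rates used in the estimation of the sample size are valid for this study".

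Section 9.9 then fixes the basis of the calculation: "The sample size re-estimation will be based on the blinded overall (not by treatment group) ECR responder rate". The timing is also defined by ECR alone: the look takes place when ECR data exist for about 60% of subjects (330). Nowhere does the protocol name the IACR success rate or the evaluability rate as an input. The detailed rules are left to an IAC charter, which is not among the documents.

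On planning, Section 9.2 states that "there is 80% power for demonstration of NI for IACR at the TOC Visit using a 10% NI margin", against more than 90% for ECR with a 12.5% margin. Section 9.6.1 requires both mITT and CE-TOC to clear -10% for the EMA conclusion, using adjusted "95% CIs calculated using the method of Miettinen-Nurminen".

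**The concern.** The stated purpose covers two endpoints and the stated input covers one. ECR is a symptom-based response at about 96 hours in the ITT set. IACR is an investigator judgement at TOC in two other sets, one of which depends on how many subjects prove clinically evaluable. The protocol gives no relation from which an IACR rate could be inferred from ECR, and evaluability does not enter ECR at all.

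IACR is also the endpoint that sets the sample size. If its success rate or the evaluability rate falls below plan while ECR is on plan, the interim would report the sample size as adequate, and the EMA comparison would go forward under-powered after a look described as having secured it.

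**Working it through.** **Inputs** (Sections 9.2 and 9.6.1, Table 11): one-sided alpha 0.025; 550 subjects, 275 per arm; ECR 79%, margin 12.5%; IACR 80% in mITT and 85% in CE-TOC, margin 10%; evaluability 80%, so 440 in CE-TOC (220 per arm). Equal true rates in the two arms are assumed, since one rate is given per set.

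**Formula.** Power = Φ((margin − c)/√(2p(1−p)/n) − 1.96), with n per arm. With c = 1/n (continuity correction) it reproduces Table 11. With c = 0 it is closer to the EMA analysis, because Miettinen-Nurminen has no continuity correction. Values with c = 0 are in square brackets throughout.

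**Reproducing Table 11**

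| Set | n per arm | p | √(2p(1−p)/n) | Power | Stated |
|---|---|---|---|---|---|
| ECR, ITT | 275 | 0.79 | 0.03474 | 93.75% [94.94%] | 93.8% |
| IACR, mITT | 275 | 0.80 | 0.03411 | 80.65% [83.44%] | 80.6% |
| IACR, CE-TOC | 220 | 0.85 | 0.03405 | 80.06% [83.58%] | 80% |

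Example, CE-TOC: (0.10 − 1/220)/0.03405 − 1.96 = 0.844, and Φ(0.844) = 80.1%.

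**IACR shortfalls at 550 subjects, ECR unchanged at 79%.** Total N is the per-arm requirement divided by evaluability where it applies, rounded up and doubled. The 77% is the low end of the CE range cited in Section 9.2 (77% to 87%). CE-TOC 80% lies inside that range; mITT 75% and 70% evaluability are illustrative assumptions.

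| Scenario | Power | Total N for 80% power |
|---|---|---|
| mITT success 75% | 74.2% [77.3%] | 630 [590] |
| CE-TOC success 80% | 70.6% [74.6%] | 678 [628] |
| CE-TOC success 77% | 66.2% [70.3%] | 746 [696] |
| CE-TOC 85%, evaluability 70% (n = 192.5) | 74.1% [78.5%] | 628 [572] |

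ECR power stays at 93.8% [94.9%] in every row.

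**Where IACR power falls below 80%:** mITT success under 79.6% [77.4%], CE-TOC success under 84.97% [83.1%], or evaluability under 79.9% [72.8%].

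**What an ECR-only rule would recommend.** The protocol states no target power for the re-estimation, so two are tried.

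- *80% target.* ECR at 79% needs 366 [334]. The worst-case variance, at a rate of 50%, needs 534 [504]. No ECR rate calls for more than 550.
- *90% target.* An increase follows only if pooled ECR is below about 73.9% [71.3%]. At 72%, the low end of the ECR range cited in Section 9.2, the requirement is 574 [544, so no increase].

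**A shared shortfall can also pass.** Suppose all three rates fall by 5 points (an assumption): ECR 74%, mITT 75%, CE-TOC 80%. ECR power is still 90.1% [91.6%], and a 90% ECR target needs 550 [518]. IACR at 80% power needs 630 [590] for mITT and 678 [628] for CE-TOC.

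**The case against.** The strongest reply is that this is a wording slip. The stated purposes in Section 9.9 and the Synopsis point to both endpoints, and the Amendment 2 summary shows IACR and the EMA outcome being added to them on purpose. The sentence naming ECR may simply have been left unedited. It does not say that ECR is the sole input, and the IAC charter, which holds the statistical rules, may already use IACR. That may well be how it arose, and what happens in practice cannot be known without the charter. But the protocol itself fixes the input. A charter that follows the sentence misses IACR, and one that adds IACR departs from it, so the sentence needs correcting either way.

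A second point is that the continuity-corrected figures overstate how tight the plan is for a Miettinen-Nurminen analysis. This stands. Without the correction there are about 2.6 points to spare in mITT success, 1.9 in CE-TOC success and 7 in evaluability. That is some reserve, but none of it is monitored by an ECR-only rule.

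Third, target power, the rule for combining endpoints and the TOC data cut could properly sit in the charter. Their absence from the protocol is not the fault here. Finally, the option to enrol 626 subjects does not fill the gap: it is tied to lefamulin exposure, and several of the requirements above exceed it.

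**Conclusion.** The point holds. As written, the re-estimation cannot deliver the EMA power that Section 9.9 claims for it, because neither IACR nor evaluability enters it. In the scenarios examined, power in the affected IACR set at 550 subjects is 66% to 74% [70% to 78%], while ECR power stays near 94% and an 80% ECR target never asks for more subjects.

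The figures assume equal true rates and normal-approximation power. The bracketed values approximate the EMA analysis without its stratification. The shortfalls show what the rule would miss; they are not forecasts. The consequence is confined to EMA power: type I error, the FDA primary analysis and the validity of the EMA test are untouched. It should be fixed.

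**What to change.** Amend the input sentence in Section 9.9 so that the re-estimation uses the blinded pooled ECR rate, the blinded pooled IACR success rates at TOC in mITT and CE-TOC, and the observed evaluability rate. The final sample size should be the largest that any of these requires. Bring the IAC charter into line. State there, or in Section 9.9, the target power and how many subjects must have TOC outcomes at the look. If the sponsor prefers to keep ECR as the only input, remove the IACR check and the EMA outcome from the stated purposes in Section 9.9, and the IACR check from the Synopsis.

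The drafting cost is one sentence plus matching charter text. TOC follows the ECR assessment by roughly one to two weeks on a 7-day course, so the look either waits briefly or uses fewer subjects for IACR. A pooled mITT rate is simple to obtain. The CE-TOC and evaluability rates also need a blinded evaluability review of the interim subjects, which is real extra work. Pooled rates do not reveal the treatment difference. The remaining cost is that the interim may recommend a larger trial.
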